13. TERMINATION OF SUBJECT FROM STUDY/DISCONTINUATION OF STUDY DRUG

13.1. Criteria for Subject Termination

Subjects may be discontinued from study participation / the study drug at any time for any of the following reasons. The possible reasons for termination of study participation / study drug are as follows:

- Adverse event
- Lack of efficacy (specify; eg, no improvement in underlying condition)
- Lost to follow-up (specify)
- Withdrawal by subject (specify)
- Non-compliance with study drug (specify)
- Protocol deviation (specify)
- Death
- Pregnancy
- Other (specify)

If at any time during the course of the study, in the opinion of the Investigator, the subject may no longer safely participate due to a change in medical status (eg, experiences an AE, becomes pregnant), the subject must be discontinued from the study drug. Subjects discontinued from study drug will be discontinued from the study.

The reason for study drug discontinuation will be recorded on the appropriate CRF. In case of death, the date of death should be captured on the CRF.

Subjects who prematurely terminate the study participation will not be replaced.

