15. STATISTICS

15.1. Sample Size

A total of 300 subjects are expected to be enrolled from approximately 50 global sites, including the US and Europe. Subjects will be assigned randomly to receive SEP-363856 or active comparator in an allocation ratio of 2:1. The determination of sample size was based upon clinical considerations. The sample size of 300 subjects will provide approximately 80 subjects who are expected to complete 1 year of treatment with SEP-363856 to support sufficient long-term safety data on SEP-363856.

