In case the model above fails to converge, a spatial exponential covariance structure and a spatial power covariance structure will be assumed sequentially. The first covariance structure to yield convergence will be used in the analysis. These analyses will be based on the observed data only. Missing data will not be imputed.

Sensitivity analyses may be conducted to assess the impact of missing data on the PANSS total score and CGI-S score analysis results by deviating away from the MAR assumption; however, all efficacy analyses are exploratory in this safety study.

Relapse

Relapse will be identified programmatically and manual data review using the pre-defined criteria (specified below). The rate of relapse will be calculated as the proportion of subjects with

a relapse in the 52-week period out of the efficacy population, along with the 95% confidence interval. The time-to-relapse will be summarized descriptively and will also be presented by a Kaplan-Meier plot, with log rank test statistic.

Relapse will be defined as the earliest occurrence of any of the following:

- Worsening of > 30% PANSS total score from Baseline (Day 1) and a CGI-S score > 3.
- Hospitalization for worsening of psychosis.
- Emergence of suicidality, homicidality and/or risk of harm to self or others.
- Discontinuation from the study due to exacerbation of the underlying illness of schizophrenia.

The frequency of hospitalization due to relapse will be summarized descriptively by treatment.

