16.2.12. RELAPSE

Relapse is defined as the earliest occurrence of any of the following:

- Worsening of >30% PANSS total score from Baseline (Day 1) and a CGI-S score >3
- Hospitalization for worsening of psychosis
- Emergence of suicidality, homicidality and/or risk of harm to self or others
- Discontinuation from the study due to exacerbation of the underlying illness of schizophrenia.

PANSS and CGI-S assessments taken at both scheduled and unscheduled visits will be considered when identifying the relapse event. The percent change in PANSS total score from Baseline will be calculated as described in [Section 16.1.6](#). Occurrence of hospitalization for worsening of psychosis will be identified by medical review of the data collected on the “*Psychiatric Hospitalization*” CRF page as well as the SAEs prior to database lock. Emergence of suicidality, homicidality, and/or risk of harm to self or others will be identified as outlined in [APPENDIX 11](#). Discontinuation from the study due to exacerbation of the underlying illness of schizophrenia will be identified as an AE included in the SMQ search listed in [APPENDIX 13 that has action taken = “Drug Withdrawn”](#).

The evaluation period for relapse will be from the day of the first dose of study medication to 2 days after the day of the last dose of study medication.

The date of relapse is defined as the earliest of: the start date of the assessment at which the qualifying PANSS and CGI-S data were collected, the date of hospital admission for worsening of psychosis, the

Document: **CCI**

Author: **PPD**

Version Number: 0.6

Version Date: 30JAN2023

Template No.: CS_TP_BS016 Revision 6

Reference: CS_WI_BS005

Effective Date: 02Dec2019

date of the assessment at which a qualifying C-SSRS event is identified, the start date of the qualifying adverse event for the second and third criteria, and the last dose date for the fourth criterion.

Time-to-relapse (in days) is defined as the date of relapse – the first dose date + 1. Subjects completing/discontinuing from the study without meeting the criteria for relapse will be censored on 2 days after the last dose of study medication.

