If the event date is due to the fourth criterion and is beyond Study Day 364, it will be re-set to the date of Study Day 364. If the event date is due to one of the other three relapse criteria and is beyond Study Day 365, it will be re-set to the date of Study Day 365. A censoring date that is beyond Study Day 365 will be re-set to the date of Study Day 365.

Kaplan-Meier estimates of the median time-to-relapse and the 25th percentile and 75th percentile of time-to-relapse, along with the respective 95% confidence intervals, will be calculated. Kaplan-Meier estimate of the probability of relapse at the end of the treatment period, and its 95% confidence interval, will also be calculated. The time-to-relapse data will be presented in a Kaplan-Meier curve along with log rank test statistic. The log rank test will be used to compare the time-to-relapse (in days) between SEP-363856 50 to 100 mg/day and Quetiapine XR 400 to 800 mg/day treatment groups.

The rate of relapse will be calculated as the proportion of subjects demonstrating a relapse during the 52-week period treatment period out of the EFF population. The 95% confidence interval for the rate of relapse will also be calculated.

The frequency of hospitalizations due to relapse will be summarized by treatment group.

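### The rate of relapse is a crude on-treatment proportion of all EFF subjects: read as a 52-week risk it is too low, and it flatters the arm with worse retention

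*SAP*

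**What the plan says.** Protocol 6.3 and SAP 2.2.3 list the rate of relapse among the other efficacy endpoints, next to time to relapse and frequency of hospitalization due to relapse.

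- **Definition.** SAP 16.2.12: the rate is "calculated as the proportion of subjects demonstrating a relapse during the 52-week period treatment period out of the EFF population", with a 95% CI. Protocol 15.3.5 matches: "The rate of relapse will be calculated as the proportion of subjects with" a relapse in the 52-week period, over the efficacy population, also with a 95% CI.
- **Window.** SAP 16.2.12 evaluates relapse "from the day of the first dose of study medication to 2 days after the day of the last dose of study medication".
- **No follow-up off drug.** Protocol 13.1: "Subjects discontinued from study drug will be discontinued from the study".
- **Leavers who do count.** The fourth relapse criterion is "Discontinuation from the study due to exacerbation of the underlying illness of schizophrenia". SAP 16.2.12 identifies it as an AE on the Appendix 13 list with study drug withdrawn.
- **Time-to-event handling.** SAP 16.2.12: "Subjects completing/discontinuing from the study without meeting the criteria for relapse will be censored on 2 days after the last dose of study medication". The same section plans a log-rank test between arms, and "Kaplan-Meier estimate of the probability of relapse at the end of the treatment period, and its 95% confidence interval, will also be calculated".
- **Expected retention.** Protocol 15.1 expects 300 subjects randomized 2:1 to give "approximately 80 subjects who are expected to complete 1 year of treatment with SEP-363856".

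**The concern.** The numerator is confined to time on treatment, while the denominator is every EFF subject whatever their time on treatment. Someone who leaves at Week 6 with no qualifying event contributes 6 weeks of observation but is scored as relapse-free for 52. The result mixes two things: how often subjects relapse, and how long they stay under observation.

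This has two consequences. First, the figure labelled as the 52-week rate will sit below the Kaplan-Meier probability reported in the same section, and the lower number carries the endpoint's name with no caveat. Second, if the arms differ in retention, the arm that loses more subjects shows fewer relapses for that reason alone. Unequal retention is a live possibility: SAP 9 compares time to discontinuation between arms and expects some discontinuations for COVID-19 or conflict-related reasons.

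**Working it through.** **Inputs from the documents.** N = 300 and 2:1 allocation give 300 × 2/3 = 200 on SEP-363856. About 80 are expected to complete one year, so implied completion is 80/200 = 40%. The documents state no dropout rate, so this is an inference. They give no expected relapse rate and no completion figure for quetiapine XR.

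**Assumptions.** True 52-week relapse risk p = 10%, 20% or 30%. Constant hazards for relapse (r) and other withdrawal (d). Withdrawal independent of relapse. Relapse ends observation, so completion C is the share reaching Week 52 on treatment without relapse.

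**Formulas** (time in units of 52 weeks):

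- r = −ln(1 − p)
- r + d = −ln(C)
- crude rate = [r / (r + d)] × (1 − C)
- the Kaplan-Meier target under independent censoring is p

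**At C = 0.40**, r + d = 0.916:

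| True p | r | Crude rate | Crude / true |
|---|---|---|---|
| 10% | 0.105 | 0.105/0.916 × 0.60 = 6.9% | 0.69 |
| 20% | 0.223 | 0.223/0.916 × 0.60 = 14.6% | 0.73 |
| 30% | 0.357 | 0.357/0.916 × 0.60 = 23.4% | 0.78 |

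Per 200 subjects at p = 20%, this is about 29 relapses recorded against 40. A simulation of that case (n = 200, 4,000 runs) gave a mean crude rate of 14.7% and a mean Kaplan-Meier estimate of 20.1%.

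**Sensitivity of the 20% case:**

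- *Timing of withdrawal.* Weibull withdrawal at the same 40% completion gives 12.9% if withdrawal is early (shape 0.5) and 16.4% if it is late (shape 2).
- *Meaning of the 40%.* If it reflects withdrawal alone and relapse does not enter it, total hazard is 0.916 + 0.223 = 1.139, and the crude rate is 0.223/1.139 × (1 − 0.40 × 0.80) = 13.3%.
- *Better retention.* At 60% completion, true risks of 10%, 20% and 30% read 8.3%, 17.5% and 27.9%.

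**Between arms.** Take p = 20% in both arms, with 40% completion in one and an assumed 55% in the other. For 55%, −ln(0.55) = 0.598, so the crude rate is 0.223/0.598 × 0.45 = 16.8%, against 14.6%. The 2.2-point gap comes entirely from retention. At 40% against 60% it is 17.5 − 14.6 = 2.9 points.

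**The case against.** The strongest reply is that the plan already contains the censoring-adjusted answer. SAP 16.2.12 gives the Kaplan-Meier probability with its CI just before the crude rate, and its only between-arm relapse test is the log-rank test. The crude proportion is openly defined, is correct as the share of EFF subjects with an observed on-treatment relapse, and matches the protocol. This all stands. What remains is that the endpoint's name sits on the figure that does not estimate a 52-week risk.

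A reader might infer more than the documents support:

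- *That all early leavers count as relapse-free.* They do not. Relapses before leaving are in the numerator, and so are discontinuations that meet the exacerbation criterion.
- *That 60% of the SEP-363856 arm is wrongly scored.* In the model above, the 60% who do not finish include the relapsers. At p = 20%, leavers scored as relapse-free are 60 − 14.6 = about 45%.
- *That Kaplan-Meier is the truth.* It assumes independent censoring. Protocol 13.1 lists lack of efficacy as a reason for termination. A subject who leaves for that reason, with no Appendix 13 AE leading to withdrawal and no other criterion met, is censored, so Kaplan-Meier may itself be low.

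The size is also uncertain. The 40% is of randomized subjects. EFF requires a post-baseline PANSS or CGI-S within 9 days of the last dose, so completion within EFF may be higher and the shortfall smaller.

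**Conclusion.** The point holds in a limited form. As written, the rate of relapse is an observed on-treatment incidence under a name and period that invite reading it as a 52-week risk. On that reading it is about 22% to 31% too low in relative terms for assumed true risks of 30% down to 10%. The 20% case reads about 13% to 16%, depending on when withdrawal happens. The arm with worse retention looks better by a few points when the true risks are equal.

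These sizes rest on assumed relapse risks, 40% completion inferred from 80/200, an assumed comparator completion, and independent withdrawal. The direction needs less: with independent withdrawal, any loss of subjects without a qualifying event pulls the crude figure below the 52-week risk.

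It would be wrong to conclude that the relapse analysis as a whole is biased by this definition. The log-rank test and Kaplan-Meier probability censor early leavers and are not affected in this way. Severity is low: relapse is one of the other efficacy endpoints, and Protocol 15.3.5 describes all efficacy analyses as exploratory in this safety study.

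**What to change.** In SAP 16.2.12:

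1. Define the rate of relapse as the already planned Kaplan-Meier probability of relapse by Day 365, with its 95% CI.
2. Add the between-arm difference in that probability, with a 95% CI.
3. Keep the crude proportion, relabelled as subjects with an observed on-treatment relapse.
4. Add a sensitivity analysis that counts lack-of-efficacy discontinuations as relapse, because the Kaplan-Meier estimate depends on independent censoring.

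Protocol 15.3.5 carries the same crude definition, so align it or record the change in SAP 3.7. No new data are needed: event times, censoring rules and the Kaplan-Meier estimate are already specified. The cost is wording, a little extra analysis (the difference and the sensitivity run), and a stated relapse rate that is less favourable.

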16.2.13. MISSING DATA METHODS FOR EFFICACY VARIABLE(S)

Other than one supplementary analysis for PANSS total score (see [Section 16.1.1.3](#) (Analysis with missing PANSS item(s) imputed)), BNSS total score (see [Section 16.2.2](#)) and MADRS total score (see [Section 16.2.3](#)), Individual missing item in any scale will not be imputed.

For derived scores that depend on more than one individual item (e.g. PANSS total score, PANSS subscale scores, PANSS Marder factor scores, PANSS UPSM factor scores and UPSM total factor score, BNSS total score, BNSS subscale scores, MADRS total score, ESS total score, SLOF total score, SLOF subscale scores, EQ-5D-5L index value, and UPSA-B total score), if one or more items are missing at a visit, the derived score will be set to missing. The corresponding change from Baseline value at a given

Document: **CCI**

Author: **PPD**

Version Number: 0.6

Version Date: 30JAN2023

Template No.: CS_TP_BS016 Revision 6

Reference: CS_WI_BS005

Effective Date: 02Dec2019

post-Baseline time point will be set to missing if the Baseline derived score is missing or if the derived score at that time point is missing.

For PANSS response, any subject with a missing PANSS total score at Baseline or at any post-Baseline time point will have their PANSS response set to missing for that time point.

17 SAFETY OUTCOMES

All outputs for the safety outcomes will be based on the SAF Population.

Unless otherwise specified, the safety summary tables will include the following columns: SEP-363856 50 to 100 mg/day and Quetiapine XR 400 to 800 mg/day.

Safety data will be used in analysis irrespective of emergency treatment unblinding (see protocol Section 7.2.3).

17.1 ADVERSE EVENTS AND PRE-TREATMENT EVENTS

Adverse events (AEs) and pre-treatment events will be coded using MedDRA central coding dictionary, Version 22.0.

Any COVID-19 related Adverse Events and pre-treatment events will be identified using a pre-defined search:

Table 2: Predefined search criteria for COVID-19 related adverse events or pre-treatment events.

Lower Level Term	Lower Level Term Code	Preferred Term	Preferred Term Code	Search Criteria for COVID-19 Related Adverse Events or Pre-treatment Events
Coronavirus test positive	1007025	Coronavirus test positive	10070255	Preferred Term Code = 10070255 or 10053983
Coronavirus infection	10051905	Corona virus infection	10053983	

Document: CCI

Author: PPD

Version Number: 0.6

Version Date: 30JAN2023

Template No.: CS_TP_BS016 Revision 6

Reference: CS_WI_BS005

Effective Date: 02Dec2019

Any adverse events related to the Russia-Ukraine geopolitical conflict will be identified by the reported term containing “BCP22”.

AEs are defined as untoward medical occurrences that started at the same time of or after the first dose of study drug. Untoward medical occurrences that started prior to the first dose of study drug are pre-treatment events.

Whenever available, the time information should be accounted for in the derivation of AEs vs. pre-treatment events. In the case where time is not available, untoward medical occurrences that started on or after the day of the first dose of study drug will be considered AEs; those that started before the day of the first dose of study drug will be considered pre-treatment events.

See [APPENDIX 2](#) for handling of partial dates for AEs. In the case where it is not possible to classify an untoward medical occurrence as an AE or a pre-treatment event, it will be classified by the worst case; i.e. AE.

Unless otherwise specified, for the purpose of statistical analysis, the AEs in the 361-304 database which started within 9 days after the last dose of 361-304 study drug, will be used in table summaries. All records in the 361-304 AE database, including those that started beyond 9 days after the last dose of study drug, will be listed in data listings.

Overall summary of the incidence of all AEs, AEs related to COVID-19, AEs related to geopolitical conflict, study medication-related AEs, severe AEs, serious AEs, AEs leading to discontinuation from study, AEs leading to study medication withdrawal, AEs leading to study medication interruption, AEs leading to dose reduction, AEs leading to dose increase and AEs leading to death will be provided by treatment group. This summary will also be repeated by the geographic region, sex, age group, number of prior hospitalizations for treatment of schizophrenia, duration of schizophrenia, and BMI category subgroups.

Listings will be provided for all AEs, severe AEs, serious AEs, AEs leading to discontinuation from the study, AEs leading to study medication withdrawal, AEs leading to study medication interruption, AEs leading to dose reduction, AEs leading to dose increase, AEs leading to death, AEs of potential drug abuse and dependence and extrapyramidal AEs, and psychiatric AEs leading to discontinuation from the study (PAEDCs), AEs related to geopolitical conflict, AEs related to COVID-19. A listing of pre-treatment events will also be presented. When complete event start date and complete event end date are available, duration of AEs/pre-treatment events will be calculated as: event end date – event start date +

Document: CCI

Author: PPD

Version Number: 0.6

Version Date: 30JAN2023

Template No.: CS_TP_BS016 Revision 6

Reference: CS_WI_BS005

Effective Date: 02Dec2019

1. Duration will be presented in data listings.

For all summaries, each subject will be counted only once within each category (e.g. an AE type, a severity level, a relationship category, a duration of exposure category, a SOC, a high level term (HLT), and a PT). If not otherwise specified, all summaries will present the number and percentage of subjects as well as the number of events. For summaries by SOC and PT, AEs will be sorted by SOC based on the internationally agreed order (see [APPENDIX 10](#)) and then by PT in decreasing frequency in the “SEP-363856 50 to 100 mg/day” column. For summaries by SOC, HLT, and PT, AEs will be sorted by SOC based on the internationally agreed order and then by HLT and PT in decreasing frequency in the “SEP-363856 50 to 100 mg/day” column.

COVID-19 related pre-treatment events and AEs and geopolitical conflict related pre-treatment events and AEs will be displayed similarly as any other pre-treatment events and AEs.

17.1.1 ALL AEs

All AEs will be summarized by SOC and PT, as well as by SOC, HLT, and PT. The summary by SOC and PT will also be presented for the following subgroups: geographic region, sex, age group, number of prior hospitalizations for treatment of schizophrenia, duration of schizophrenia, and BMI category.

In addition, summary tables (by SOC and PT) will be generated for those AEs starting after the last dose of study drug and those AEs starting more than 1 day after the last dose of study drug.

AEs reported by $\geq 2.0\%$ (without rounding) of subjects in any treatment group will be summarized by SOC and PT.

Non-serious AEs reported by $>5.0\%$ (without rounding) of subjects in any treatment group will be summarized by SOC and PT.

The summary by SOC and PT will be broken down further by maximum severity, by strongest relationship to study medication and by duration of exposure to study medication at earliest onset. These summaries are described in the sections below.

17.1.1.1. Severity

Severity is classed as mild/ moderate/ severe (increasing severity). AEs with a missing severity will be classified as severe.

Document: **CCI**

Author: **PPD**

Version Number: 0.6

Version Date: 30JAN2023

Template No.: CS_TP_BS016 Revision 6

Reference: CS_WI_BS005

Effective Date: 02Dec2019

If a subject reported an AE more than once within that SOC/ PT with different severity levels, the subject will be assigned to a severity level for that SOC/ PT based on the worst case severity (i.e. maximum severity). Event counts will not be included in this summary.

In a separate table, severe AEs will be summarized by SOC and PT.

17.1.1.2. Relationship to Study Medication

Relationship to study medication, as indicated by the Investigator, is classified as “not related”/ “possible”/ “probable”/ “definite” (increasing strength of relationship). A “related” AE is defined as an AE with a relationship to study medication as “possible”, “probable” or “definite”. AEs with a missing relationship to study medication will be regarded as related to the study medication. For this summary, AEs will be presented in 2 categories, related and not related.

If a subject reported an AE more than once within the same SOC/ PT in different relationship categories, the subject will be assigned to a category for that SOC/ PT based on the worst case relationship (i.e. strongest relationship). Event counts will not be included in this summary.

In a separate table, study medication-related AEs will be summarized by SOC and PT.

17.1.1.3. Duration of Exposure

Duration of exposure to study medication at earliest onset is categorized below:

1 to 13, 14 to 27, 28 to 41, 42 to 89, 90 to 179, 180 to 269, 270 to 359 and ≥ 360 days.

If a subject reported an AE more than once within the same SOC/ PT in different exposure categories, the subject will be assigned to a category for that SOC/ PT based on the earliest onset. Event counts will not be included in this summary.

Denominators for exposure intervals will be based on the number of subjects who were exposed as of the first day of the interval. For cases where events start after the last dose, the exposure interval for the event will be considered the interval of the last day of exposure to study medication.

